Our objective is to determine if using Optison echocardiography contrast increases sensitivity and specificity of detecting left atrial appendage thrombus in transesophageal echocardiography studies as opposed to standard 2D and 3D TEE imaging without the use of echo contrast.

Study Population

Age of Participants: 18+

Sample Size:

At Utah: 500
All Centers: 500

Inclusion Criteria:

Patients referred to the University of Utah Echocardiography Lab for a transesophageal echocardiography (TEE) will be included in the study.

Subjects must be

- (1) > 18 years old
- (2) Able to provide consent
- (3) Indicated for TEE as a standard clinical procedure to evaluate cardiac health status

Exclusion Criteria:

- Patients will be excluded for meeting the contraindications for Optison administration.
1. Known right-to-left, or bi-directional cardiac shunts.
 2. Hypersensitivity to perflutren, blood, blood products or albumin.
 3. Women who pregnant (since Optison may have effects on the fetus that are currently unknown).
 4. Removal of Left Atrial Appendage.
 5. Not able to provide Informed Consent.

Design

Prospective Clinical Research

Study Procedures

Recruitment/Participant Identification Process:

Potential participants for the study will be recruited from the Cardiology/Electrophysiology (EP) clinic during normally scheduled clinic visits. No other recruitment procedures (phone call / recruitment letters) will be used in this study. In-person contact by the PI /sub-I or other cardiologists (made aware of study by word of mouth) who refer their patients into the study will be the primary mode of recruitment. Prior to approaching the subject, the PI/research staff will conduct a chart review to confirm that the potential subject fits the eligibility criteria for the study.

Potential participants will be screened by the PI/Co-PI and other cardiologists who are aware of the study and refer the subject to the study. When the patient is being seen in the clinic for a routine follow-up visit, if the patient fits with all the eligibility criteria during chart review (prior to clinician seeing the patient), then the PI/sub-I/ clinician will approach the potential participant and discuss the study with them.

If the potential subject is interested in participation, the PI/Co-PI will consent the subject or call the Study Coordinator (SC) /Clinical Research Manager (CRM) to conduct the informed consent process with the participant. The PI/sub-I may be present during the process. However, if they are not able to be physically present, the SC /CRM will report to the PI/Sub-I immediately after consent to confirm the appropriate conduct of the process.

Informed Consent:

Description of location(s) where consent will be obtained:

University of Utah Hospital and Clinics, specifically the ECHO clinic.

Description of the consent process(es), including the timing of consent:

Patients will be approached at the University of Utah Hospital and Clinics on the day that they are already scheduled to undergo their standard of care TEE for their specific clinical problem. If patients are found to fit with the eligibility criteria outlined for the study, they will be approached and the study discussed with them. The clinician may consent the patient themselves, or call the study coordinator / clinical research manager to conduct the consent process. The person who is conducting the consent process will provide a detailed description of the study, the study-related procedures, time that the participant will have to spend for the study, the benefits and risks of participation, the costs and compensations involved in the study, the contacts for the PI, IRB and the research participant advocate. The University of Utah's stand on research-related injuries will be explained and the participant's questions will be answered. The participant will be provided with a copy of the consent form and given as much time as they require to go over the consent and to make an informed decision. Participants who require extra time will be given the option to call the study team back. All this information and the consent process will be documented in the staff notes section of each participant's folder. If the study coordinator / clinical research manager conduct the informed consent process, then the PI / sub-I who identified the eligible participant will sign the informed consent form right below the signature of the person who conducted the informed consent process after confirmation that the informed consent process was completed in an appropriate and satisfactory manner.

Procedures:

1. Patients will be identified and pre-screened using electronic medical records. Final screening and consent will be conducted in clinic, generally on the day that they were already scheduled to undergo a standard of care TEE for their specific clinical condition.
2. If the patient is found to be eligible based on inclusion/exclusion criteria, the investigator and/or study coordinator will approach them and explain the study.
3. If the patient agrees to participate and provides informed consent, then we fill out an enrollment sheet, create their study file and gather the necessary information from the patient.

4. Patient will then undergo their scheduled TEE without optison contrast. The clinician will determine whether it is possible to clearly identify the presence or absence of left atrial appendage thrombus from the standard TEE images.

5. If the presence or absence of thrombus cannot be clearly determined with standard TEE, the clinician will administer optison contrast and then continue the examination to try to obtain a conclusive result.

6. Data will then be collected, including ECHO reports, cardiac MRI reports, medical history, adverse events etc. as compiled during the procedure visit. Data will only be collected if the patient receives Optison during the TEE procedure.

7. Three months following the TEE, the medical record of the patients that received Optison will be reviewed for any additional adverse events or thrombii detection via other method. The end point of the study will be the collection of pertinent data, three months following TEE.

Statistical analysis will be conducted utilizing the statistical resources available to us through the CCTS.

Optison will be used for its approved indications (as an ultrasound contrast agent) and in compliance with the U.S. Food and Drug Administration (FDA) safety guidelines. Optison is a contrast agent used in ECHO studies, and does not involve any radiation/radioactive substances. The ECHO procedure does not expose patients to ionizing radiation, and Optison or ultra sound contrast agents do not contain dye or increase a patient's risk of nephrotoxicity. Ultrasound contrast agents are safe and completely radiation-free diagnostic imaging tools.

Procedures performed for research purposes only:

Administration of Optison echocardiography contrast and re-imaging using standard 2 and 3D techniques will be the research-related procedure. The participant will be undergoing the Echocardiography for clinical indications and additional echo with optis contrast will be provided along with participant's clinical echo.

Statistical Methods, Data Analysis and Interpretation

Descriptive presentation of continuous variables and chi-squared / Fisher-exact tests for frequency variables. Since this study is a descriptive, pilot study to see utility of Optison in echocardiography, the contrast agent will be used in 100 patients to see at what

frequency the contrast agent is able to identify LAA thrombi. The contrast agent is already being used in echo, we are using it as it is approved by the FDA. A future larger RCT study will be construed using this pilot data.

While we intend to gather optison TEE data from 100 subjects, our enrollment cap has to be higher than that. Only those subjects whose standard TEE's are inconclusive will be administered optison, and subjects will need to be consented prior to the start of the standard TEE. Because only a minority of enrolled patients will receive optison, we plan to enroll 500 patients.

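### The objective is a gain in sensitivity and specificity over standard TEE, but data are kept only when standard TEE was inconclusive and no uniform reference test is required, so the gain cannot be estimated

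*Combined protocol and SAP*

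**What the plan says.** The opening paragraph of the Combined protocol and SAP sets one objective: to "determine if using Optison echocardiography contrast increases sensitivity and specificity of detecting left atrial appendage thrombus in transesophageal echocardiography studies". The comparator named there is 2D and 3D TEE without contrast.

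The Procedures section then fixes who is studied and what is kept:

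- Step 4: each consented patient first has the standard TEE, and the clinician judges whether it settles the thrombus question.
- Step 5: "If the presence or absence of thrombus cannot be clearly determined with standard TEE, the clinician will administer optison contrast". Statistical Methods, Data Analysis and Interpretation repeats this: "Only those subjects whose standard TEE's are inconclusive will be administered optison".
- Step 6: "Data will only be collected if the patient receives Optison during the TEE procedure". The material gathered is described as "including ECHO reports, cardiac MRI reports, medical history, adverse events etc. as compiled during the procedure visit".
- Step 7: at three months, the records of Optison recipients "will be reviewed for any additional adverse events or thrombii detection via other method".

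The only research-specific procedure listed is Optison with re-imaging; no reference test appears. The statistical section plans descriptive summaries with chi-squared or Fisher tests and says that "this study is a descriptive, pilot study to see utility of Optison in echocardiography". It names one outcome, the "frequency the contrast agent is able to identify LAA thrombi", and plans 100 Optison examinations from 500 enrolled patients.

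**The concern.** Comparing the accuracy of two tests needs a result from each test and the true disease status, in patients not selected on the result of one of them. The plan meets neither condition.

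- **Comparator.** Every retained patient is there because standard TEE gave no clear answer. The true and false positives and negatives of standard TEE all lie among patients whose results are not collected.
- **Disease status.** MRI reports are gathered but no MRI is required. The three-month review picks up whatever other test happened to be done, with no test or timing fixed.
- **Named outcome.** How often Optison identifies thrombi is neither sensitivity nor specificity. Read literally, it also gives no credit for clearly ruling thrombus out, which is half of what step 5 seeks.

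At stake is the trial's only stated objective. Any accuracy change it reported would reflect an unstated convention, and the protocol intends to build a larger RCT on these data.

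**Working it through.** **1. The plan's own figures.** 100/500 = 20% are expected to receive Optison. 500 - 100 = 400 patients (80%) have a conclusive standard TEE whose result is not collected. The documents give no power calculation, thrombus prevalence, inconclusive rate or accuracy, so there is nothing further to reproduce. Rates used below are assumptions for illustration.

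**2. Head-to-head comparison in the retained patients.** Assume 100 Optison patients, 10 with thrombus. Optison calls 8 of the 10 thrombi (sensitivity 80%) and wrongly calls 9 of the 90 others (specificity 81/90 = 90%). The standard TEE figures then depend only on how an inconclusive reading is scored:

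| Inconclusive scored as | Standard sensitivity | Standard specificity | Change in sensitivity | Change in specificity |
|---|---|---|---|---|
| Negative | 0/10 = 0% | 90/90 = 100% | +80 | -10 |
| Positive | 10/10 = 100% | 0/90 = 0% | -20 | +90 |
| Failure in both groups | 0% | 0% | +80 | +90 |
| Excluded | undefined | undefined | undefined | undefined |

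The data do not change from row to row, yet the sign of the answer does. The third row cannot show anything but a gain, because selection sets both standard figures to zero.

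**3. Add-on comparison (standard TEE, then Optison if inconclusive).** Score inconclusive as a miss. The gain in sensitivity is the extra thrombi found divided by all thrombi among the 500. With 8 extra thrombi:

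- 25 thrombi in total: 8/25 = 32 points
- 50 in total: 8/50 = 16 points
- 100 in total: 8/100 = 8 points

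That total is not collected.

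**4. Optison's own accuracy in the subset.** Without disease status, 10 positive and 90 negative calls fit very different truths equally well: sensitivity and specificity of 10/10 and 90/90, of 9/10 and 89/90 (0.90 and 0.99), or of 5/20 and 75/80 (0.25 and 0.94).

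Partial verification does not settle it. Assume true sensitivity 0.80, specificity 0.95 and 10% prevalence, so that per 100 patients TP = 8, FN = 2, FP = 4.5 and TN = 85.5. If 80% of positives but only 10% of negatives are verified:

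- naive sensitivity = 6.4/(6.4 + 0.2) = 0.97
- naive specificity = 8.55/(8.55 + 3.6) = 0.70

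With 30% of negatives verified, they are 6.4/(6.4 + 0.6) = 0.91 and 25.65/(25.65 + 3.6) = 0.88.

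**5. The named frequency.** Using the step 2 rates:

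| Prevalence in subset | All positive calls per 100 | True thrombi only per 100 |
|---|---|---|
| 5% | 4 + 9.5 = 13.5 | 4 |
| 10% | 8 + 9 = 17 | 8 |
| 20% | 16 + 8 = 24 | 16 |

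The first count rises with false positives; the second is capped by prevalence. Neither sees rule-outs. If Optison calls 10 thrombi and rules out 80, it scores 10/100, the same as if it calls 10 and rules out none. The proportions resolved are 90/100 (exact 95% CI 82.4% to 95.1%) and 10/100 (4.9% to 17.6%). This pair is deliberately extreme.

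**The case against.** The strongest defence is that the statistical section calls this a descriptive pilot and plans no accuracy test. That is true, but the opening paragraph still states an accuracy objective, so the label confirms the mismatch rather than removing it.

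Four narrower points deserve an answer.

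- **Data on the other 400.** Step 3 opens a study file for everyone who consents, so it is too strong to say these patients have no data at all. What stands is that the file precedes the TEE, while steps 6 and 7 limit imaging reports and follow-up to Optison recipients. The 80% also assumes exactly 500 enrolled and 100 given Optison.
- **Add-on direction.** If inconclusive counts as a miss, adding Optison cannot lower sensitivity, so the direction is known in advance. Its size, which would be the finding, is what is lost.
- **Reading of the outcome.** The named frequency is loosely worded and may have been meant to include rule-outs, which might be recoverable from the echo reports. The protocol does not say so, and the outcome needs defining either way.
- **Another remedy.** The accuracy question could be kept by recording standard TEE results for all 500 and applying one prespecified reference test regardless of TEE result. That is a valid route, but it adds procedures that the present plan does not contain.

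A remark elsewhere in the statistical section that contrast echo is supplied with the clinical echo might suggest that everyone receives Optison. Steps 5 and 6 and that section's closing paragraph exclude this.

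**Conclusion.** The concern holds. The stated comparison of sensitivity and specificity cannot be estimated from the data the protocol keeps. This follows from the eligibility for contrast, the data-collection rule and the absence of a required reference test, and needs no assumed rate. On the planned figures, 80% of enrolled patients contribute no standard TEE result. The point changes in accuracy, the add-on gains and the frequency figures are illustrations on assumed rates. They show that both the sign and the size of any reported change would depend on choices or totals the trial does not supply. Because this is the only stated objective, it must be corrected.

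**What to change.** Restate the objective and primary outcome as follows: among patients whose standard TEE is inconclusive for LAA thrombus, the proportion in whom Optison-enhanced TEE gives a conclusive result, present or absent, with an exact 95% confidence interval. Count examinations still inconclusive after Optison as not resolved, and report present and absent calls separately. This matches the aim already set in step 5.

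Three safeguards should accompany it:

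- The proportion also rises with confident wrong calls. Cross-tabulate each call against the MRI and three-month information already collected, give the number verified, and describe the verification as non-uniform.
- Remove the claim of increased sensitivity and specificity from the objective and from any conclusions.
- State that, without a control, the yield cannot separate the effect of contrast from that of a second look. State also that the result rests on the clinician's own judgement of what is conclusive.

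The cost is protocol wording, one recorded field (present, absent or still inconclusive after Optison) and one extra table. No patients or procedures are added. The claim becomes narrower, but 100 patients give usable precision: the exact 95% interval is 39.8% to 60.2% at 50/100 and 70.8% to 87.3% at 80/100.

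### No present/absent call is specified before Optison, so standard TEE has 0% conclusive yield by selection and no reading to compare in the analysed patients

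*Combined protocol and SAP*

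**What the plan says.** The objective at the head of the combined protocol and SAP is to "determine if using Optison echocardiography contrast increases sensitivity and specificity of detecting left atrial appendage thrombus", judged against 2D and 3D TEE without contrast.

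Under Study Procedures, Procedures:

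- Step 4, on the standard TEE images: "The clinician will determine whether it is possible to clearly identify the presence or absence of left atrial appendage thrombus".
- Step 5: where the answer "cannot be clearly determined with standard TEE", "the clinician will administer optison contrast and then continue the examination to try to obtain a conclusive result".
- Step 6: "Data will then be collected, including ECHO reports, cardiac MRI reports, medical history, adverse events etc". It then restricts the data set: "Data will only be collected if the patient receives Optison during the TEE procedure".
- Step 7, at three months: "the medical record of the patients that received Optison will be reviewed for any additional adverse events or thrombii detection via other method".

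Statistical Methods, Data Analysis and Interpretation repeats the selection rule: "Only those subjects whose standard TEE's are inconclusive will be administered optison". It aims for 100 Optison recipients out of 500 enrolled, calls the study a descriptive pilot that will inform a later randomised trial, and names chi-squared and Fisher's exact tests for frequencies.

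Nowhere do the documents specify a confidence or image-quality scale, criteria for an inconclusive examination, a separate or blinded read, or a present/absent call made before contrast.

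**The concern.** A comparison of two imaging methods needs a reading from each. In the patients whose data are kept, the only standard-TEE result that the procedures define is that thrombus could be neither clearly seen nor clearly excluded. Two consequences follow.

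First, standard TEE starts from no conclusive examinations because of how patients are chosen. Any yield measure (examinations made conclusive, or thrombi newly identified) can then only stay level or improve after Optison.

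Second, without a present/absent call before contrast, the sensitivity and specificity of standard TEE in this set depend entirely on how an inconclusive examination is coded. Nobody can see whether Optison confirmed or reversed what the clinician would otherwise have said.

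In addition, the judgement that admits a patient and the judgement after contrast appear to be made by the same person, who knows that contrast was given. The yield then reflects that reader's threshold for doubt as well as any effect of Optison. The later randomised trial would be planned from that mixture, and an impression that was never recorded cannot be reliably recovered afterwards.

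**Working it through.** **Inputs.** From the documents: 100 intended recipients, 500 enrolled, Optison and data collection only after an inconclusive standard TEE, chi-squared or Fisher's exact tests. Assumed here because the documents give no figure: a two-sided 5% level, the share q of examinations that a second look alone would resolve, and the accuracy example in step 4.

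**1. The plan's own figures.** There is no power or precision calculation to reproduce. The two sample sizes imply an inconclusive share of 100/500 = 20%, which is not stated. The point does not depend on it.

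**2. Yield before and after.** Let x of 100 recipients be conclusive after Optison.

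| | Conclusive after | Inconclusive after |
|---|---|---|
| Conclusive before | 0 (by selection) | 0 (by selection) |
| Inconclusive before | x | 100 − x |

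The change in yield is x/100 − 0/100, which cannot be negative. The cell for examinations made worse is empty before any data are collected.

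**3. What a test of that table would do.** Exact McNemar with all discordance one way: p = 2 × 0.5^x. Fisher's exact test, the one the plan names, compares 0/100 with x/100 (it ignores the pairing).

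| x | Fisher p | Exact McNemar p |
|---|---|---|
| 5 | 0.059 | 0.063 |
| 6 | 0.029 | 0.031 |

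Six resolved examinations would suffice. If Optison did nothing and continued looking alone resolved a share q, the chance of at least 6 is P(X ≥ 6) with X ~ Binomial(100, q):

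| q (assumed) | P(X ≥ 6) |
|---|---|
| 2% | 0.02 |
| 5% | 0.38 |
| 10% | 0.94 |
| 20% | about 1.00 |

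**4. Sensitivity and specificity without a pre-contrast call.** Illustration: 10 patients with thrombus and 90 without. Optison gives 8 true positives, 5 false positives and 80 true negatives. The other 90 − 5 − 80 = 5 patients without thrombus stay inconclusive.

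| Coding of inconclusive | Standard sens. | Standard spec. | Optison sens. | Optison spec. |
|---|---|---|---|---|
| Not positive | 0/10 = 0% | 90/90 = 100% | 8/10 = 80% | 85/90 = 94% |
| Error | 0/10 = 0% | 0/90 = 0% | 8/10 = 80% | 80/90 = 89% |

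Standard specificity is 100% or 0% on the same patients. Under the first coding specificity moves against Optison; under the second it can only rise. The coding rule decides the comparison, and the plan gives none.

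**5. Reader threshold.** How many examinations were called inconclusive because of a low bar for doubt is not observable without a graded call before contrast. No figure in the documents bounds it.

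**The case against.** The strongest reply is that this is a descriptive pilot of an add-on test. Giving contrast only to unresolved examinations is a recognisable design, the statistics section asks how often contrast identifies thrombi, and no before-and-after test is explicitly planned. That stands to this extent: the significance figures above describe what would happen if the named tests were applied to yield, not something the plan commits to. It does not answer the stated objective, which is comparative, or the intention to build a randomised trial on these data.

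It can also be said that echo reports are collected and no data form is shown, so a pre-contrast impression might be recorded. The accurate statement is that none is specified.

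A reader might go further in four ways that the documents do not support:

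- **That every result can only favour Optison.** True of yield, not of specificity, which false positives can lower. Cardiac MRI reports and the three-month review could also contradict an Optison reading, although neither is systematic or named as a reference standard.
- **That the same clinician declares the examination resolved.** Step 5 speaks only of trying for a conclusive result, so examinations may stay inconclusive. It does not say who makes the post-contrast call; one clinician is the natural reading.
- **That the unblinded reader causes the 0% baseline.** Selection causes it. Perfect blinded grading of the same subset would still start from 0%. The reader adds a separate bias through the threshold.
- **That an observed resolution rate can be discounted to a true one.** Suppose 80 of 100 are resolved and 20 would have been called correctly on a forced read. The rate among the other 80 lies anywhere from 60/80 = 75% to 80/80 = 100%. With 50 such examinations it lies from 30/50 = 60% to 50/50 = 100%. These sums also treat a lucky guess as a resolved examination and need a reference standard that the plan lacks.

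**Conclusion.** The point holds in this form. Followed as written, steps 4 to 6 leave standard TEE without a usable present/absent reading in the analysed set, so the comparison of sensitivity and specificity in the objective cannot be made there. Conclusive yield on standard TEE is fixed at 0% by selection and can only stay level or rise. That the yield also depends on one reader's threshold rests on the natural reading of step 5, and its size cannot be derived from the documents. The significance results rest on the assumed 5% level and assumed values of q; the accuracy example is illustrative only.

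This is a cheap improvement to a pilot. It does not make the design a diagnostic accuracy study.

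**What to change.** Amend steps 4 to 6 of the Procedures:

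1. Before Optison is given, the clinician records and time-stamps a forced best call (present or absent), a five-level confidence grade (definitely absent, probably absent, cannot say, probably present, definitely present) and the reason the examination is inconclusive. The same form is completed after Optison.
2. State that the grade documents the existing decision to give contrast and does not govern it. Who receives Optison is unchanged.

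Add to the statistical section:

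3. Report descriptively how many calls were confirmed, reversed or still uncertain.
4. Use McNemar's test only on the paired forced present/absent calls, where changes in both directions are possible. Describe it as a shift in positivity, not in accuracy.
5. Set both calls against the cardiac MRI reports and the three-month review where these exist, and say how many patients have them.
6. Do not test before-and-after conclusiveness or the shift in confidence grades, because selection fixes the baseline of both.

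Cost: one short form, about a minute for each of roughly 100 Optison recipients, with no extra reader, patients or procedures. Limits: the clinician completing the second form still knows the first call and that contrast was given, so observer bias is reduced, not removed. The form supplies no reference standard and no data on patients whose standard TEE was conclusive.

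### Optison and further imaging are given as one package after an inconclusive exam, but the result is credited to the contrast agent alone

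*Combined protocol and SAP*

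**What the plan says.** The objective at the start of the protocol is comparative: sensitivity and specificity for left atrial appendage (LAA) thrombus with Optison, "as opposed to standard 2D and 3D TEE imaging without the use of echo contrast".

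The order of work is in Procedures, steps 4 and 5. First, "Patient will then undergo their scheduled TEE without optison contrast". Then "The clinician will determine whether it is possible to clearly identify the presence or absence of left atrial appendage thrombus" from those images. If that is not possible, the clinician gives Optison and is then to "continue the examination to try to obtain a conclusive result". The section on procedures performed for research purposes only describes the intervention as a combination: "Administration of Optison echocardiography contrast and re-imaging using standard 2 and 3D techniques will be the research-related procedure".

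The Statistical Methods section calls the study a descriptive pilot in 100 patients given contrast, and names as its result the "frequency the contrast agent is able to identify LAA thrombi". It adds that a larger RCT will be built on these data. Step 6 limits the dataset: "Data will only be collected if the patient receives Optison during the TEE procedure".

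The documents do not ask for the LAA views obtained before contrast to be logged. They do not ask which view gave the answer afterwards, and they include no further look without contrast.

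**The concern.** The intervention has two parts, contrast and more imaging, but the result is worded as the effect of one. Selection makes this matter. Only exams already judged inconclusive receive Optison, so the resolved share before contrast is zero by construction, and any later resolution can only show up as gain. Some of that gain could come from the clinician looking again, or from a view not obtained the first time. With no control group, and no data kept from exams without Optison, the plan has no means of telling these apart.

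What is at stake is what the pilot can conclude about Optison, and how its figure is used in planning the RCT.

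**Working it through.** **The plan's own figures.** The plan gives 100 patients with contrast out of 500 enrolled, and 100/500 = 0.20. The documents say only that a minority will receive Optison, so 20% is a back-calculation and not a stated inconclusive rate. The point does not depend on it.

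**Inputs.**
- n = 100 patients given Optison (Statistical Methods).
- Resolved before contrast: 0 of 100, by selection (step 5).
- r = share of inconclusive exams that a further look without contrast would settle. Not in the documents; assumed 0.10 to 0.30.
- t = share of the remainder settled only because of contrast. Not in the documents; assumed 0, 0.30 or 0.50.

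**Formulas.**
- Yield credited to contrast = r + (1 − r)t.
- Part that contrast adds over a further look = (1 − r)t, so the credited yield exceeds it by r.
- Excess of the credited yield over t = r(1 − t).

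Example with r = 0.20 and t = 0.30: credited 0.20 + 0.80 × 0.30 = 0.44; added by contrast 0.80 × 0.30 = 0.24; excess over t 0.20 × 0.70 = 0.14.

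| r | t | Credited | Exact 95% CI, n = 100 | Added by contrast | Excess over t |
|---|---|---|---|---|---|
| 0.10 | 0 | 10% | 4.9–17.6% | 0 | 10 points |
| 0.20 | 0 | 20% | 12.7–29.2% | 0 | 20 points |
| 0.30 | 0 | 30% | 21.2–40.0% | 0 | 30 points |
| 0.10 | 0.30 | 37% | 27.6–47.2% | 27% | 7 points |
| 0.20 | 0.30 | 44% | 34.1–54.3% | 24% | 14 points |
| 0.30 | 0.30 | 51% | 40.8–61.1% | 21% | 21 points |
| 0.10 | 0.50 | 55% | 44.7–65.0% | 45% | 5 points |
| 0.20 | 0.50 | 60% | 49.7–69.7% | 40% | 10 points |
| 0.30 | 0.50 | 65% | 54.8–74.3% | 35% | 15 points |

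The confidence interval describes sampling error around the credited yield and does not cover this bias. The bias is zero if r = 0, and the design cannot check r.

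**Which outcome this describes.** The table is written for resolution, meaning thrombus found or excluded. The result named in the plan is thrombus found. The same formulas apply if r and t are read as shares in which thrombus is found, but those shares cannot exceed the resolution shares, so the table must not be read as the size of the error in the thrombus frequency.

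**Can other planned data recover r?** Step 6 keeps nothing from patients not given Optison. Step 7 reviews the records at three months for thrombi found by other methods. That may show whether a final read was right, but not whether contrast or the further look produced it.

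**The case against.** The best defence is that adding contrast after an inconclusive exam is a sensible pragmatic sequence for a descriptive pilot, and that the protocol openly defines the research procedure as Optison with re-imaging. Both points stand. They lower the stakes, and they show that the wording of the result, more than the sequence, needs to change. They do not remove the mismatch, because the objective is comparative and the Statistical Methods section names only the contrast agent.

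Three stronger readings are tempting, and the documents do not support them:

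- *A reader might infer that contrast interrupts an unfinished standard exam.* Step 4 places the scheduled TEE and the clinician's verdict before contrast, and the later text speaks of re-imaging and of an echo added to the clinical one. The natural reading is that the standard exam comes first. The word continue in step 5, and the lack of a completeness rule, leave the other reading open but do not establish it.
- *A reader might infer that imaging goes on until an answer is found.* Step 5 says the clinician tries for a conclusive result, which allows an inconclusive end.
- *A reader might infer that the RCT will be under-sized.* The documents give no endpoint, comparator, effect size or sizing method for it. Under-sizing would follow only if this before/after yield were taken as the contrast effect, for instance against a control arm given equal further imaging.

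It is also fair to say that a log of views cannot separate contrast from a second look at the same views. That stands, and it is why the claim itself has to be restated.

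**Conclusion.** The point holds as one of attribution. Optison and further imaging are given together to exams selected as inconclusive, without a control, and the yield is assigned to contrast. Any exam settled by the second look or by a new view would be counted for Optison.

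The number of such exams is unknown and could be near zero. The figures above rest entirely on assumed values of r and t: over r = 0.10 to 0.30, the credited yield exceeds what contrast adds by 10 to 30 points. This is a cheap improvement, not a flaw that invalidates the pilot.

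**What to change.** 1. In the Statistical Methods section, and wherever the RCT is planned from these data, state the result as the yield of Optison plus repeat imaging after an inconclusive standard TEE, not of Optison alone.
2. For each patient given Optison, store the LAA views obtained and the clinician's read before contrast, and record which views gave the post-contrast answer.
3. Beside the main result, report the yield separately for answers from views already obtained before contrast and for answers from new views only. Treat this as a descriptive sensitivity result: discounting new views could under-credit Optison where contrast is what made the view readable.

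The log documents what was imaged. It should not set a rule for when contrast may be given. It needs to be in place from the start, because views not logged at the time cannot be reliably reconstructed later.

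Cost: a short view log, one analysis line and a somewhat weaker claim. No extra patients and no second arm are needed.
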